6.3 Assignment of Subject Identification Numbers

Each subject who consents will be assigned a unique subject identification number (SID), which identifies the subject for all clinical trial-related procedures. SIDs are a combination of a 4-digit site code and a 4-digit subject number. After SIDs are assigned, they cannot be reused or reassigned for any reason. Information regarding the SID and screen date will be documented on a screening and enrollment log/system and in the CRF.

Previously screen failed subjects may be rescreened provided there is a valid documented reason for rescreening (i.e. changes to the person's health or situation that would make them possibly eligible at this later time). If rescreening occurs, the subject will keep their original Subject ID.

6.4 **SAFETY EVALUATIONS**

PHYSICAL AND TARGETED PHYSICAL EXAM

INO-4800	COVID19-311
Inovio Pharmaceuticals, Inc.	Clinical Protocol

A full physical examination will be conducted during Screening and at study discharge/EOS (e.g. Day 393). A targeted physical assessment will be performed at other visits as determined by the Investigator based on subject symptoms.

VITAL SIGNS

Vital signs including temperature, respiration rate, blood pressure and heart rate will be measured at Screening and at visits specified in the Schedule of Events (Tables 3 and 4.).

At the COVID-19 assessment and convalescent visits, temperature, respiration rate, heart rate and oxygen saturation should be performed.

HEIGHT AND WEIGHT

Weight and height will be collected at Screening.

SOCIO-BEHAVIORAL ASSESSMENT

A Socio-behavioral Assessment, including self-reported smoking and vaping history, and self-reported history of exposure to second-hand smoke will be obtained at Screening.

LABORATORY EVALUATIONS

Blood samples will be collected at visits specified in the Schedule of Events (Tables 3 and 4.). A total of approximately mL 245-330mL of blood will be drawn from each subject over the course of the study (inclusive of relevant safety and immunology samples at regular study visits per Tables 3 and 4). If the subjects is evaluated at COVID-19 visits, an additional volume of approximately 85-120mL will be collected. Subjects may be asked to return for additional blood draws if collected blood sample is lost or unevaluable for any reason.

Hematology [Complete blood count (CBC) with automated differential]:

White blood cell (WBC) count, red blood cell (RBC) count, hemoglobin, hematocrit and platelet count will be measured at Screening (Phase 2 segment only) and at visits specified in the Schedule of Events (Tables 3 and 4.). Hemoglobin A1c will additionally be performed at Screening (Phase 2 segment only).

Serum chemistry:

Electrolytes [Sodium (Na), Potassium (K), Chloride (Cl), Bicarbonate (HCO3), Calcium (Ca), Phosphate (PO4)], glucose, Blood Urea Nitrogen (BUN), Creatinine (Cr), alkaline phosphatase, aspartate aminotransferase (AST), alanine aminotransferase (ALT), LDH, and total bilirubin (TBili) at Screening (Phase 2 segment only) and at visits specified in the Schedule of Events (Tables 3 and 4.).

Urinalysis:

Urine samples will be tested by dipstick for glucose, protein, and hematuria at Screening (Phase 2 segment only) and at visits specified in the Schedule of Events (Tables 3 and 4). If abnormal (presence of protein, hematuria, or glucose \geq 1+), a microscopic examination should be performed.

Serology:

HIV antibody or rapid test will be measured at Day 0 only.

Antibodies to SARS-CoV-2 will be measured at Screening and at visits specified in the Schedule of Events (Tables 3 and 4).

Pregnancy Testing:

INO-4800	COVID19-311
Inovio Pharmaceuticals, Inc.	Clinical Protocol

Pregnancy testing will be performed on women of childbearing potential (WOCBP). All women will be assumed to be of childbearing potential unless they are:

- Women who are post-menopausal as defined by reported spontaneous amenorrhea for ≥ 12 months;
- Women who are surgically sterile or have a partner who is sterile (i.e., vasectomy in males or tubal ligation, absence of ovaries and/or uterus in females). In the case of a vasectomy, subjects should wait six (6) months post-vasectomy to be considered sterile.

Phase 2: For WOCBP, a serum pregnancy test will be obtained at Screening and a urine pregnancy test will be performed immediately prior to any dosing and at the subject's last visit.

Phase 3: For WOCBP, a urine pregnancy test will be obtained at Screening and will be performed immediately prior to any dosing.

A negative result for urine β -HCG (test must have a sensitivity of at least 25 mlU/mL) must be available prior to each administration of IP. If the β -HCG test is positive, indicating that the subject is pregnant prior to completing the specified dose regimen, then no further IP will be administered. Every attempt should be made to follow pregnant subjects for the remainder of the study and to determine the outcome of the pregnancy (see Section 7.12).

DIARY

Diaries will be implemented in the Phase 2 segment of the protocol and at selected sites (estimated to include 711 subjects) in the Phase 3 segment. Subjects will be provided a diary to record the following solicited local and systemic AEs:

- Oral temperature and time taken (each daily entry before 11:59 pm)
- Solicited systemic symptoms
- Solicited local injection site symptoms
- Concomitant medications

The diary should be completed once daily starting the evening of each study dose through 6 days post-dose. The completed diary post-dose 1 and post-dose 2 will be reviewed with the subject by the study staff during the next study phone call or visit and collected at the next in-person study visit. The study staff will review the diary with the subject to assess for temperature, solicited systemic symptoms (unusually tired/feeling unwell, muscle aches, headache, nausea, joint pain) and solicited injection site symptoms (pain, itching, redness, swelling, bruising). In addition, unsolicited symptoms and concomitant medications will be assessed.

Any diary entry determined to meet the Common Terminology Criteria for Adverse Events version 5.0 (CTCAE) criteria for a Grade 1 or higher adverse event should be documented as an adverse event unless deemed part of the subject's ongoing medical history. Injection site reactions should be graded per the Toxicity Grading Scale for Healthy Adult and Adolescent Volunteers Enrolled in Preventive Vaccine Clinical Trials, issued September 2007 (See Section 6.4.5). If the diary entry does not meet the criteria of a Grade 1 or higher AE as per the relevant guidelines, Investigator clinical judgment can be used to determine whether the entry should be recorded as an AE and documented accordingly in the site's source. For cases where the diary entry and final AE reporting (i.e. grading) do not agree, the reasoning should be recorded in the source documents.

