Physical Exam ^b	Х	Х			Х		Х		Х		Х		Х		Х	Х	Х
Vital Signs	Х	Х			Х		Х		Х		Х		Х		Х	X ⁿ	Xn
Height and Weight	Х																
HIV Serology		Х															
Pregnancy Test ^c	Х	Х			Х												
INO-4800 or Placebo + EP ^d		Х			Х												
Download EP Data ^e			Х			Х											
Adverse Events ^f	Х	Х	Х	Х	Х	Х	Х	Х	Х	Х	Х	Х	Х	Х	Х	Х	Х
Cellular Samples ^g		Х					Х				Х				Х	Xr	Х
Humoral Samples ^h		Х					Х				Х				Х	Xr	Х
SARS-CoV-2 Serology ⁱ	Х	Х			Х		Х		Х		Х		Х		Х		Х
SARS-CoV-2 RT-PCR		х														X٥	
(Nasopharyngeal swabs)		^														^	
Distribute Diary ^p			Х			Х											
Review/Collect Diary ^q				Х	Х		Х										

a. Screening assessment occurs from -30 days to -1 day of Day 0. Screening and Day 0 visits may be combined if eligibility is able to be confirmed prior to dosing. If so, all assessments for Screening and Day 0 must be performed at the combined visit.

b. Full physical examination only at Screening and Day 393 (or EOS). Targeted physical exam at other indicated visits.

COVID19-311 Protocol | VV-TMF-00448 | 5.0

INO-4800 Inovio Pharmaceuticals, Inc.

COVID19-311 Clinical Protocol

- c. In women of childbearing potential. Urine pregnancy test at all indicated visits.
- d. Intradermal injection(s) in skin preferably over deltoid region, or alternately over anterolateral quadriceps region, followed by EP at Day 0 and Day 28.
- e. Following administration of INO-4800 or placebo, EP data will be downloaded from the CELLECTRA® 2000 device and provided to Inovio.
- f. AEs to be collected from time of consent to Day 56; SAEs, MAAEs, and AESIs to be collected from time of consent to EOS.
- g. On Day 0, cellular sampling requires 64 mL of whole blood prior to 1st dose. At all other time points, collect 32 mL of whole blood. Cellular samples will be collected at selected clinical sites (estimated to include 711 subjects)
- h. On Day 0, humoral sampling requires a total of 17 mL of whole blood (two 10-mL red top serum collection tubes, each 8.5 mL of whole blood, to produce four serum aliquots of 2 mL each). At all other time points, collect 8.5 mL of whole blood in a single 10-mL red top serum collection tube to produce two serum aliquots of 2 mL each.
- i. SARS-CoV-2 antibody.
- j. The Day 0 RT-PCR results will not be required prior to dosing on that day.
- k. Day 42 visit must occur at least 10 days after Day 28 visit.

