 - ICD or pacemaker (to prevent a life-threatening arrhythmia) that is located ipsilateral to the deltoid injection site (unless deemed acceptable by a cardiologist);
 - Any metal implants or implantable medical device within the electroporation site;
- k. Blood donation or transfusion within 1 month prior to Day 0;
- I. Prisoners or subjects who are compulsorily detained (involuntary incarceration);
- m. Reported alcohol or substance abuse/dependence or illicit drug use (excluding marijuana use) within the prior 2 years;
- n. Any illness or condition that in the opinion of the investigator may affect the safety of the subject or the evaluation of any study endpoint.

4.2.2 **PHASE 3 SEGMENT**

- Acute febrile illness with temperature ≥100.4°F (38.0°C) or acute onset of upper or lower respiratory tract symptoms (e.g., cough, shortness of breath, sore throat) on Day 0 prior to dosing;
- Positive serologic test for SARS-CoV-2 at Screening (after approximately 402 subjects positive for SARS-CoV-2 serologic test are randomized, this criterion will apply to all remaining subjects);
- c. Pregnant or breastfeeding, or intending to become pregnant or intending to father children starting from the Screening visit until the last dose;
- d. Positive urine pregnancy test during screening or immediately prior to dosing;
- e. Known history of uncontrolled HIV based on a CD4 count less than 200 cells/mm³ or a detectable viral load within 3 months prior to screening;
- f. Is currently participating or has participated in a study with an investigational product within 30 days prior to Day 0 (documented receipt of placebo in a previous trial would be permissible for trial eligibility);
- g. Previous or planned receipt of an investigational (including Emergency Use Authorization (EUA) or local equivalent authorization) or licensed vaccine for prevention or treatment of COVID-19, MERS or SARS (documented receipt of placebo in previous trial would be permissible for trial eligibility);
- h. Immunosuppression as a result of underlying illness or treatment including:
 - Primary immunodeficiencies (conditions including hypothyroidism, Hashimoto's thyroiditis and vitiligo are allowed);

INO-4800	COVID19-311
Inovio Pharmaceuticals, Inc.	Clinical Protocol

- Long term use (≥7 days) of oral or parenteral glucocorticoids at a dose of ≥20 mg/day of prednisone equivalent (use of inhaled, topical, nasal, otic, and ophthalmic corticosteroids are allowed) in the past 6 months;

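### Section 6.4 counts a woman with a sterile partner as not of childbearing potential, so it requires no pregnancy test before dosing for some women whose own fertility is intact, and other parts of the protocol do not match this

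*Protocol*

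**What the plan says.** All references are to version 5.0 of the protocol.

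- **Who is tested.** Section 6.4, under Pregnancy Testing, opens with "Pregnancy testing will be performed on women of childbearing potential (WOCBP". It then sets a default, "All women will be assumed to be of childbearing potential unless they are" in one of two listed groups. The first is post-menopausal women. The second is "Women who are surgically sterile or have a partner who is sterile (i.e., vasectomy in males", continuing with female causes of sterility and a six-month wait after vasectomy.
- **What is tested.** For Phase 2: "For WOCBP, a serum pregnancy test will be obtained at Screening", with urine tests before dosing and at the last visit. For Phase 3: "For WOCBP, a urine pregnancy test will be obtained at Screening and will be performed immediately prior to any dosing".
- **Schedules of Events.** Table 4 footnote c (Phase 3) repeats the limit: "In women of childbearing potential. Urine pregnancy test at all indicated visits". Table 3 footnote e (Phase 2) gives only the specimen type by visit and has no such limit.
- **Visit lists.** Sections 6.1.1 (Screening) and 6.1.2.1 (Day 0 and Day 28) list the pregnancy test without restriction and refer to Section 6.4.
- **Negative result.** Section 6.4 closes the topic by saying that a negative urine beta-HCG "must be available prior to each administration of IP". It states no exemption.
- **Eligibility.** Phase 3 exclusion d (Section 4.2.2) is "Positive urine pregnancy test during screening or immediately prior to dosing". Inclusion b and exclusion c separately require that a woman not be pregnant. Partner sterility also appears in the reproductive-capacity criteria (4.1.1 g and 4.1.2 f.2), as one way of meeting them alongside effective contraception.

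**The concern.** The same circumstance does two different jobs. In the inclusion criteria, a sterile partner is an alternative to using contraception, which is a sensible place for it. In Section 6.4 it decides whether the woman herself can conceive, which it does not describe. Women who rely on hormonal methods, an intrauterine device or abstinence (4.1.2 f.3) remain of childbearing potential and are tested. Women who rely on a partner's sterility are not, and no reason is given for the difference.

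Pregnancy is an exclusion (4.2.2 c) and a reason to stop dosing (4.3, 6.4, 7.12), and effects on a fetus or pregnancy are listed as a theoretical risk (1.4.2.2). The pre-dose test is the control that brings these rules into play before product and electroporation are given. For one definable group of women Section 6.4 does not require that control, while other passages list it for everyone. Two sites could read the same protocol and act differently.

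**Working it through.** The protocol gives no figure on this point, so the check is a comparison of passages.

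**Step 1. Classification.** Take a premenopausal woman who has not been sterilised and whose partner has had a vasectomy at least six months ago. Under Section 6.4 every woman starts as of childbearing potential. The second exempt group joins her own surgical sterility and her partner's sterility with an *or*, so the partner's status alone is enough. She is classed as not of childbearing potential.

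**Step 2. Tests required by Section 6.4.** Both segment rules are limited to women of childbearing potential. None of the tests they schedule is required for her:

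| Segment | Scheduled tests | Where |
|---|---|---|
| Phase 2 | Screening (serum), Day 0, Day 28, Day 393 | Section 6.4; Table 3 |
| Phase 3 | Screening, Day 0, Day 28 (urine) | Section 6.4; Table 4 |

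In Phase 3, Screening and Day 0 may be one visit (Table 4 footnote a), so three scheduled tests is a maximum.

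**Step 3. The other passages, for the same woman.**

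| Place | Limited to childbearing potential? |
|---|---|
| Section 6.4, segment testing rules | Yes |
| Table 4 footnote c | Yes |
| Table 3 footnote e | No |
| Sections 6.1.1 and 6.1.2.1, visit lists | No, but they refer to Section 6.4 |
| Section 6.4, negative result before each administration | No exemption stated |
| 4.2.2 exclusion d | Needs a test result to operate |
| 4.1.2 inclusion b; 4.2.2 exclusion c | No; they apply to her without a required test |

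**Step 4. Result.** Section 6.4 and footnote c leave her outside required testing. The visit lists and Table 3 footnote e would include her if read by themselves. If she is not tested, exclusion d has nothing to act on, and no negative result exists for the closing sentence of Section 6.4.

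**Step 5. Can the group be counted?** Table 2 plans 3357 + 201 = 3558 subjects aged 18-50 out of 7116, which is half. The protocol gives neither the share who are women nor the share of women with a sterile partner, so a count would rest on two assumed proportions.

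**The case against.** The strongest reply is that the negative-result sentence closes a subsection devoted to women of childbearing potential. Taken with no scope at all it would also demand a negative test from men and post-menopausal women. The natural reading is that women who are tested need a negative result. This stands. A reader might infer a flat contradiction inside Section 6.4, and the text does not support one. What survives is a definition that leaves a group with intact fertility outside required testing, and other passages that do not carry the same limit.

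A reader might also infer that these women go untested. That is too strong. No passage forbids testing them, the visit lists name the test for all, and Section 6.0 allows procedures at unscheduled times when the investigator judges them clinically necessary. The most the text supports is that Section 6.4 does not require a test.

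Nor does eligibility hang on the test alone. Inclusion b and exclusion c bind every woman, and Section 7.12 stops further product once site staff know of a pregnancy. These rules stand, but they depend on a pregnancy being known, and an early one may not be.

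It is tempting to say that the clause was carried over from the inclusion criteria by mistake. The wording is close but adapted: in the criteria the six-month wait is tied to enrolment, in Section 6.4 to being regarded as sterile. The documents do not show whether this was deliberate.

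Finally, pregnancy is less likely in women with a sterile partner. Any head-count of untested women would not be a count of exposed pregnancies.

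**Conclusion.** The point holds as a gap in a definition and an inconsistency between sections. Section 6.4 uses a contraceptive circumstance to define childbearing potential. As a result it and Table 4 footnote c require no Screening or pre-dose pregnancy test for a premenopausal, non-sterilised woman with a sterile partner, while the visit lists, Table 3 footnote e, the negative-result requirement and exclusion d are not written with that exemption.

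It does not affect fertile women in general, and it does not show that any pregnant woman would be dosed. The efficacy analysis and its error rates are untouched. The size of the group cannot be derived from the documents, and the number of pregnancies exposed still less. The conclusion rests only on reading the *or* in the exemption as written. It is worth correcting because it weakens a safety control without a stated reason and invites differing practice across sites.

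**What to change.** Reconcile the childbearing-potential definition in Section 6.4 and Table 4 footnote c with the negative-result requirement in Section 6.4, the visit lists in Sections 6.1.1 and 6.1.2.1, Table 3 footnote e and exclusion d. The outcome should be one stated testing population, worded the same in every place, applied at all sites and consistent with the requirement for a negative result before dosing. If the exemption for partner sterility is intended, the reason should be given and the negative-result sentence and visit lists should state the same scope. Who must be tested is a clinical decision for the sponsor and is not proposed here.

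The cost is an edit to one definition and a few cross-references. If the reconciliation widens the tested group, the already scheduled test (urine, except serum at Phase 2 Screening) is run in some additional women.

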Please refer to the Investigator's Brochure and User Manual, which will include future updates of the risk profile through the duration of the study.

1.4.1 **POTENTIAL BENEFITS**

The efficacy of INO-4800 remains unknown.

1.4.2 **PRODUCT RISKS**

1.4.2.1. Expected Risks of INO-4800 Delivered ID followed by EP using the CELLECTRA® 2000 Device

In accordance with the International Council for Harmonisation (ICH), Inovio-sponsored studies have been designed to minimize risk to study participants. Expected risks of INO-4800 delivered ID followed by EP with the CELLECTRA[®] 2000 device are listed below in Table5.

Table 5: Expected Risks of INO-4800 Delivered ID followed by EP using the CELLECTRA® 2000 Device^a

Frequency among subjects ^b	Event
Very Common (≥10%)	 Injection site pruritus Injection site erythema or redness Injection site pain^c or tenderness
Common (≥1% to <10%)	Injection site bruisingInjection site swelling or induration
Uncommon or Rare (<1%)	 Administration site lesions or bleeding Temporary severe injection site pain or tenderness

^a Investigator's Brochure v3.0, dated 25-Aug-2020

^b EU commission guideline on the SmPC September 2009 [58]

° Brief muscle contractions may occur and could be uncomfortable

1.4.2.2 Theoretical Risks of INO-4800 Delivered ID followed by EP using the CELLECTRA® 2000 Device

The following adverse events have been observed at least once, as of June 30, 2020, across all clinical trials with Inovio DNA products delivered intradermally followed by EP using the CELLECTRA[®] 2000 device:

Allergic reaction

INO-4800	COVID19-311
Inovio Pharmaceuticals, Inc.	Clinical Protocol

- Anxiety
- Creatine phosphokinase (CPK) elevations that are transient
- Injection site infection, paresthesia, hypoesthesia, hematoma, or scab
- Vasovagal reaction, lightheadedness or dizziness.

The following events have not been observed, as of June 30, 2020, in any subject or any clinical trials with Inovio DNA products delivered intradermally followed by EP using the CELLECTRA[®] 2000 device. While considered theoretical and unlikely to occur, any occurrence of these events should be reported to the Sponsor during this trial:

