6.4.5 ASSESSMENT OF INJECTION SITE REACTIONS

Reactions arising from the IP administration procedure may be reported as administration site or injection site reactions. When evaluating administration (injection) site reactions throughout the study, it is most important to be as specific as possible by selecting the most appropriate term (see Table 10 below) and using the grading scale as listed in the Toxicity Grading Scale for Healthy Adult and Adolescent Volunteers Enrolled in Preventive Vaccine Clinical Trials, issued September 2007. All subjects will be observed for 30 minutes following the IP administration procedure for immediate AEs. In addition, other events associated with administration (injection) site reactions (e.g., hematoma, infection or necrosis) should also be reported with preferred terms specific for administration (injection) site reactions.

INO-4800
Inovio Pharmaceuticals, Inc.

Local Reaction to Injectable Product (Grade)	Mild (1)	Moderate (2)	Severe (3)	Potentially Life Threatening (4)
Pain	Does not interfere with activity	Repeated use of non- narcotic pain reliever >24 hours or interferes with activity	Any use of narcotic pain reliever or prevents daily activity	Emergency room visit or hospitalization
Tenderness	Mild discomfort to touch	Discomfort with movement	Significant discomfort at rest	ER visit or hospitalization
Erythema/Redness ^a	2.5-5 cm	5.1-10 cm	>10 cm	Necrosis or exfoliative dermatitis
Induration/Swelling ^b	2.5-5 cm and no interference w/ activity	5.1-10 cm or interferes with activity	>10 cm or prevents daily activity	Necrosis

Table 10: Grading Scale for Injection Site Reactions

September 2007 "FDA Guidance for Industry-Toxicity Grading Scale for Healthy Adult and Adolescent Volunteers Enrolled in Preventive Vaccine Clinical Trials"

^a In addition to grading the measured local reaction at the greatest single diameter, the measurement should be recorded as a continuous variable

^b Should be evaluated and graded using the functional scale as well as the actual measurement.

6.4.6 **CONCOMITANT MEDICATIONS/TREATMENTS**

All medications (prescription and nonprescription) taken at the time of Screening and ongoing from signing of the informed consent to study discharge that do not affect a subject's eligibility for participation (see Section 4.2) must be recorded on CRFs.

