7.10.3 Assessing Severity (Intensity)

Severity is used to describe the intensity of a specific event (e.g., mild, moderate, severe).

The Investigator will assess and grade clinical AEs or SAEs (based on discussions with clinical trial subjects) in accordance with CTCAE.

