8.5.3 SAFETY ANALYSES

8.5.3.1 Adverse Events

All AEs including injection-site reactions will be summarized among the Safety Population by frequency per treatment arm. These frequencies will be presented overall and separately by dose, and will depict overall, by system organ class and by preferred term, the percentage of subjects affected. Additional frequencies will be presented with respect to maximum severity and to strongest relationship to Study Treatment. Multiple occurrences of the same AE will be counted only once following a worst-case approach with respect to severity and relationship to Study Treatment. All serious AEs will also be summarized as above.

The main summary of safety data will be based on events occurring within 30 days of any dose. For this summary, the frequency of preferred term events will be compared between study arms with risk differences and 95% confidence intervals, using the method of Miettinen and Nurminen. As this analysis will use many event categories, and produce many confidence intervals, caution should be exercised when interpreting these confidence intervals. Separate summaries will be based on events occurring within 7 days of any dose and regardless of when they occurred.

The analyses listed above will be performed according to Phase. For the Phase 3 segment, the analyses listed above will also be performed according to SARS-CoV-2 serostatus at baseline.

For AE data, partial start dates will be imputed to the date of treatment to conservatively report the event as treatment-emergent, whenever the portion of the date is consistent with that of the study treatment. Otherwise, it will be imputed to the earliest date consistent with the partial date. A completely missing onset date will be imputed as the

INO-4800	COVID19-311
Inovio Pharmaceuticals, Inc.	Clinical Protocol

day of treatment. Partial stop dates will be assumed to be the latest possible day consistent with the partial date. AE duration will be calculated as (Stop Date – Start Date) + 1.

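### Local reactogenicity (endpoint 1a): no stated scale grades itching and bruising, sub-Grade 1 diary entries become AEs at investigator judgment, and only AEs are summarised

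*Protocol*

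**What the plan says.** All references are to the protocol, version 5.0. Secondary endpoint 1a in both segments is the incidence of solicited and unsolicited injection site reactions (Section 3.4, Table 7). Solicited reactions come from a diary, used in Phase 2 and at selected Phase 3 sites with an estimated 711 subjects.

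- **Section 6.4, Diary.** Staff review the "solicited injection site symptoms (pain, itching, redness, swelling, bruising". Any entry at CTCAE v5.0 Grade 1 or higher is to be documented as an AE, unless it belongs to the subject's ongoing medical history. The next sentence reads: "Injection site reactions should be graded per the Toxicity Grading Scale for Healthy Adult and Adolescent Volunteers Enrolled in Preventive Vaccine Clinical Trials". If an entry is below Grade 1 on the relevant guidelines, "Investigator clinical judgment can be used to determine whether the entry should be recorded as an AE". Where the diary and the final AE grading disagree, the reason goes into the source documents.
- **Section 6.4.5.** Reactions are to be given the most appropriate term from Table 10, "using the grading scale as listed in the Toxicity Grading Scale for Healthy Adult and Adolescent Volunteers Enrolled in Preventive Vaccine Clinical Trials". The table, "Table 10: Grading Scale for Injection Site Reactions", has four rows: pain, tenderness, erythema/redness and induration/swelling.
- **Sections 7.1 and 7.10.3.** Safety in general is graded on CTCAE v5.0, and investigators grade clinical AEs from discussions with "clinical trial subjects) in accordance with CTCAE".
- **Section 8.5.3.1.** "All AEs including injection-site reactions will be summarized among the Safety Population by frequency per treatment arm", with further tables by maximum severity. No tabulation of the diary entries themselves is described.

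**The concern.** Two of the five solicited local reactions do not appear on the scale named for local reactions. A third and a fourth, redness and swelling, appear on it only above a size or functional threshold. CTCAE is named beside that scale with no rule for which one prevails. Entries under the threshold then pass through an investigator decision with no criteria, and the analysis section describes only what comes out as AEs.

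At stake are the absolute incidence and severity of local reactions, which is what endpoint 1a reports. The gap concerns reactions the protocol itself expects: Table 5 lists injection site pruritus as very common (at least 10%) and bruising as common (1% to under 10%). Section 1.3.5 reports that the one related Phase 1 event above Grade 1 was an injection site pruritus of Grade 2, without naming the scale. In Phase 2 the Week 8 safety data also feed the choice between one and two injections per visit.

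**Working it through.** The protocol states no figure that could be reproduced here. The check compares the texts, followed by an illustration of scale.

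**Step 1. Solicited reactions against Table 10**

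| Solicited in diary (6.4) | Row in Table 10 (6.4.5) | Lowest graded finding |
|---|---|---|
| Pain | Yes | Pain that does not interfere with activity |
| Itching | None | None |
| Redness | Yes | 2.5 cm |
| Swelling | Yes | 2.5 cm, or interference with activity at any size |
| Bruising | None | None |

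Two of five have no row. The fourth row of the table, tenderness, is not among the solicited items.

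**Step 2. Which scale governs?** Section 6.4 applies CTCAE Grade 1 to any diary entry and in the next sentence assigns injection site reactions to the 2007 scale. Sections 7.1 and 7.10.3 apply CTCAE generally. No section says which scale grades itching or bruising, or which prevails where the two differ. The documents do not show whether or how CTCAE v5.0 grades these two symptoms, so nothing here rests on that.

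**Step 3. Route into the analysis.** An entry at Grade 1 or higher becomes an AE. An entry below Grade 1 becomes an AE only if the investigator so judges. Section 8.5.3.1 counts AEs. A diary entry not recorded as an AE therefore has no stated route into endpoint 1a. One site can record every report of itching under CTCAE. Another can find no Table 10 grade, treat the entry as below Grade 1 and use judgment.

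**Step 4. Illustration of scale.** Inputs are 711 diary subjects (Section 6.4), 2:1 allocation (Section 8.7) and the Table 5 frequencies. I assume that the 2:1 ratio holds within the diary sites and that the Table 5 frequency is what the diary would show. The share of entries recorded as AEs is also assumed, because the protocol gives none.

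- INO-4800 diary subjects: 711 × 2/3 = 474.
- Itching at the 10% floor: 474 × 0.10 = 47.4, about 47 subjects.
- Apparent incidence = diary incidence × share recorded.

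| Share recorded | Itching as AE, subjects | Apparent incidence |
|---|---|---|
| 100% | 47 | 10% |
| 75% | 36 | 7.5% |
| 50% | 24 | 5% |
| 25% | 12 | 2.5% |

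For bruising at 1% to just under 10%, full recording gives about 5 to 47 subjects (474 × 0.01 = 4.7; 474 × 0.10 = 47.4). Half recording gives about 2 to 24. These figures show how far the count could move. They are not evidence that entries will go unrecorded.

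**The case against.** The strongest reply is that the recording rule is not empty. The CTCAE sentence covers any diary entry, itching and bruising included, and discretion opens only below Grade 1. Against a strict Grade 1 rule, that discretion can only add events. Section 6.4.5 does not treat the four rows as a closed list: other administration site events, hematoma among the examples, are also to be reported. Footnote a of Table 10 has the redness measurement kept as a continuous variable, so small redness is not lost as data. Disagreements between diary and AE record must be explained in source. Both arms receive injection plus electroporation under blinding.

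Most of this stands, and it rules out three stronger readings that a reader might infer.

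- *Itching and bruising become AEs only at the investigator's discretion, with no grade available.* The CTCAE threshold in the same paragraph contradicts this. A missing Table 10 row does not by itself make an entry ungraded.
- *The endpoint is under-counted.* The text shows a possible shortfall relative to all diary entries, not an actual one.
- *The comparison between arms is biased.* Nothing in the protocol supports this, and blinding makes differential recording less likely.

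The reply does not remove the conflict over scales or supply criteria for the judgment. An explanation filed in source does not put the event into a table. Nor can a later analysis plan settle it fully: grading and recording are done at the sites as data are collected, and Section 8.1 presents Section 8 as the formal analysis plan.

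**Conclusion.** The point holds as an ambiguity in grading and counting. For itching and bruising the protocol does not say which scale applies. Table 10 gives no grade to redness under 2.5 cm, or to swelling under 2.5 cm without interference with activity. Entries judged below Grade 1 reach the endpoint 1a tables only through uncriteried judgment. The incidence and severity reported can therefore differ between sites for identical diaries, and can be lower than the diary recorded.

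The size is unknown. The illustrated range for itching, 10% down to 2.5%, rests on the Table 5 floor and on assumed recording shares of 100% to 25%. The efficacy analysis is not affected. This is a worthwhile and inexpensive improvement to the reactogenicity reporting.

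**What to change.** 1. In Section 8.5.3.1, add a table for endpoint 1a built directly from the diary: any occurrence of each of the five solicited local reactions, by arm and by dose, with redness and swelling under 2.5 cm shown as a separate category. Present it beside the AE summary, which stays as planned.
2. Reconcile Sections 6.4 (Diary), 6.4.5, 7.1 and 7.10.3 by naming the one scale that grades each of the five solicited local reactions, itching and bruising included.

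The cost is wording in those sections and one extra table. The diary entries are already collected. The small-size category needs the redness and swelling measurements that the Table 10 footnotes call for to be held in the database. The other consequence is that reported reactogenicity may look less favourable than under the AE summary alone.
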